6.2 Identification of subjects

Subjects with a diagnosis of standard HER-2/neu-positive IBC or HER-2 2+ but FISH negative with Stage IIIA \geq N2, or have recurrent HER-2 positive metastatic breast cancer rendered NED by any means that have completed chemotherapy and/or trastuzumab will be recruited from the Rowan Breast Center. Up to 18 patients will be enrolled in this Pilot Phase I trial. No exceptions to eligibility will be made.

Fifteen subjects were enrolled at Rowan Breast Center.

Study Schema: Adjuvant HER2+

Inclusion Criteria

- 1. Women ≥ 18 years.
- Subjects with Invasive Breast Cancer at least Stage IIIA ≥ N2 (>4 positive nodes) or have recurrent metastatic breast cancer rendered NED by any means that are classic HER-2 3+ 10%, 2+ IHC and FISH positive or HER-2 2+ FISH negative that have completed chemotherapy and/or trastuzumab and have no evidence of disease.

Version v2 03/01/2017

Pilot Phase I HER-2 Pulsed DC Vaccine to Prevent Recurrence for Patients with HER-2 Driven High Risk Invasive Breast Cancer

- 3. Patients deemed to require anti-estrogen therapy for treatment of their breast cancer can continue anti-estrogen therapy during vaccinations
- 4. Women of childbearing age with a negative pregnancy test documented prior to enrollment.
- 5. Patients with ECOG Performance Status Score of 0 or 1 (Appendix D).

- 6. Women of childbearing potential must agree to use a medically acceptable form of birth control (medically accepted methods: birth control pills, condoms and spermicidal lubricants, intrauterine device, and diaphragm) during their participation in the study.
- 7. Subjects who have voluntarily signed a written Informed Consent in accordance with institutional policies after its contents have been fully explained to them.

Exclusion Criteria

- 1. Pregnant or lactating females.
- 2. Subjects with positive HIV or hepatitis C at baseline
- 3. Subjects with coagulopathies, including thrombocytopenia with platelet count <75,000, INR > 1.5 and partial thromboplastin time > 50 sec
- 4. Subjects with major cardiac illness MUGA < 50% EF.
- 5. Subjects with pre-existing medical illnesses or medications which might interfere with the study as determined by PI.

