Between 8 and 21 days post vaccine the patient will return for the sixth vaccination. Again a history and physical exam will be taken. Any changes in history or physical will be documented. Ultrasound (US) guided intranodal delivered vaccines will be administered in the NIH Clinical Research Center at Penn or the Clinical Research unit at Moffitt Cancer Center by a radiologist or sonographer experience in ultrasound guidance and the principal investigators or his/her designee.

Each dose will consist of between $1.0-2.0 \times 10^7$ cells and will be injected into 1-2 different normal groin lymph nodes or axillary nodes.

O. Post vaccine assessment

Subjects will be administered the vaccines and observed. All subjects with vaccine related AEs will be followed until the AE has resolved to baseline. Vital signs will be obtained prior to the vaccination and again 15 minutes after the dose is given. Subjects with no noted complications will then be discharged. The anticipated complication could be fever. If an Adverse Event is observed, the subject observation time will be revised appropriately. A physician familiar with the study will be readily available in the event of any complication and such subjects will be transferred to an appropriate care unit for further monitoring and treatment. Similarly any discharged subject who develops symptoms will be promptly re-evaluated and admitted for care if inpatient hospitalization is deemed necessary by the PI or his/her designees.

P. Administration of Additional Boost Vaccines.

After the subject has completed 6 vaccines, they will undergo leukapheresis to obtain lymphocyte and monocyte fractions, if needed.

Q. Administration of First Boost Vaccine

Approximately 3 months from completion of the induction vaccines, subjects will receive 3 boost vaccines at approximately 3 month intervals. Again a history and physical exam will be taken. Any changes in history or physical will be documented. Ultrasound (US) guided intranodal delivered vaccines will be administered in the NIH Clinical Research Center at Penn or the Clinical Research unit at Moffitt Cancer Center by a radiologist or sonographer experience in ultrasound guidance and the principal investigators or his/her designee. Each dose will consist of between $1.0-2.0 \times 10^7$ cells and will be injected into 1-2 different normal groin lymph nodes or axillary nodes

R. Post vaccine assessment

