Toxicity will be graded according to the NCI-CTCAE version 4.02

C. Toxicity Definition for Leukapheresis

Grade 1: Requirement for oral calcium supplementation either during or just after procedure. Severe bruising requiring treatment such as warm compresses or anti-inflammatory medication for a brief 1 week duration.

Grade 2: Prolonged requirement for calcium administration greater than 24 hours, infection at the intravenous site requiring treatment or intervention with antibiotics or surgery.

Grade 3: Alteration in vital signs such as severe hypotension requiring hospitalization, hospitalization secondary to infection.

D. Dose Limiting Toxicity (DLT)

Since the agent being administered is a biologic agent prepared from the subjects own cells as opposed to a single drug we will lump the toxicity together as that caused by the process of preparation of the DC vaccine. A subject that develops any grade 3 or greater toxicity per the NIH Cancer Therapy Evaluation Program Common Toxicity Criteria version 4.03 except for fever greater than 40° C for <12 hours will be taken off protocol. A continuous monitoring rule for

dose-limiting toxicity will be followed during the trial, as described in section 6.11 Statistical Considerations.

Grade 2 allergic reaction: generalized urticaria Greater than or equal Grade 3 allergic reaction Greater than or equal Grade 2 autoimmune reaction Greater than or equal Grade 3 cardiac toxicity Any Greater than or equal Grade 3 hematologic and non-hematologic toxicity. Greater than or equal Grade 2 toxicity for leukapheresis

E. Adverse Events

Adverse events will be graded according to NCI Common Toxicity Criteria (version 4.03 seehttps://evs.nci.nih.gov/ftp1/CTCAE/About.html. A copy is enclosed in the Appendix.

1. Adverse Event Reporting

All adverse events will whether or not associated with the study agents be recorded on the CRF. Adverse Events will be reported to the IRB, Data Safety and Monitoring Committee (DSMC), Moffitt Cancer Center Protocol Monitoring Committee (PMC);Safety Monitoring Committee, GCRC, FDA, and NIH. The information collected includes:

•The time of onset of any new adverse event or worsening of a previous adverse event

- •The specific type of adverse reaction in standard medical terminology
- •The duration of the adverse event
- •The grade of the adverse event
- •The attribution of the adverse event to the study reagents

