6.9 Statistical Considerations

6.9.1 Design. A single arm phase I trial of HER-2 pulsed DC1 vaccine in subjects with high risk HER-2^{pos} breast cancer with residual disease after neoadjuvant therapy. Subjects will receive 6 weekly DC1 vaccinations and may then be eligible to receive up to 3 boost vaccinations given every 3 months. This study will enroll 18 evaluable subjects. Evaluable implies that a subject received all 6 weekly vaccinations and underwent leukapheresis after the vaccinations for immune response evaluation. Subjects will be followed for 30 days after their *final* vaccination.

6.9.2 Objectives. The primary objectives are to determine feasibility and safety. The secondary objectives are to evaluate immunogenicity and anti-HER2 immunity.

6.9.3 Endpoints. Feasibility is defined as a subject's ability and willingness to complete the treatment regimen (6 weekly vaccinations). Safety is established by grading the observed toxicities using CTC Version 3.0. Cardiac toxicity due to trastuzumab will be monitored 2 weeks after the sixth weekly vaccination (week 8) and at EOS and scored separately from vaccinerelated toxicity. Cardiac toxicity is defined as either asymptomatic change in MUGA (i.e., >20% decline in EF by repeat echo or EF <50%) or symptomatic EF drop or heart failure. Doselimiting toxicity (DLT) due to vaccination is defined as: Grade 2 allergic reaction/generalized urticaria, > Grade 3 allergic reaction/other, > Grade 2 autoimmune reaction, > Grade 2 cardiac toxicity or as specified above, > Grade 3 hematologic and non-hematologic toxicity (except fever) and > Grade 2 toxicity due to leukapheresis. DLT rate will be defined by the weekly vaccination schedule. Toxicities will be scored separately for the maintenance boost schedule. Immunogenicity is evaluated with descriptive statistics and box plots for multiple CD4+ and CD8+ T cell metrics obtained at baseline, 2 weeks after the sixth weekly vaccination (week 8) and after each maintenance boost, as show in the table below. Immune response (IR) is defined as >2 fold increase relative to baseline. Anti-HER2 response will be a quantitated by dilution studies. Long-term anti-HER2 immunity will be assessed at follow-up visits (e.g., q 6 months).

Immune Parameter	Assay Method	Fold change	Response (>2 fold ↑)
Peptide specific reactivities	Tetramer	~	\checkmark
CD8+ T cell activation or tumor recognition	cytokine release	~	\checkmark

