CD4+ T cell activation	ELISPOT	~	\checkmark
Overall immune response	(response to any of a	above)	

6.9.4 Monitoring Unacceptable Toxicity. Early termination rules for asymptomatic and symptomatic cardiac toxicity and vaccine-related dose-limiting toxicity have been defined for monitoring purposes. Toxicity data will likely be reviewed after groups of 3 women have been treated. Enrollment will be terminated if data indicate that the rate of 1) asymptomatic cardiac toxicity >20%, 2) symptomatic cardiac toxicity/heart failure >5% or 3) vaccine-related DLT rate >25%. For cardiac toxicity, we assume an uninformative beta (1, 1) prior and for vaccine-related DLT we assume a modestly informative beta (1, 3) prior since safety of our DC1 vaccine has been established in >50 women treated on our DCIS trials. Given the prior and the observed data, the Bayesian posterior probability that the toxicity rate exceeds the specified rate, is calculated. If the numbers of subjects with toxicity equals or exceeds the numbers (in shaded rows) in the table below, then it is likely that the toxicity rate is unacceptable, as noted by Bayesian posterior probabilities.

Bayesian Early Termination Rules for Cardiac Toxicity Rate							
Subjects treated	3	6	9	12			
Subjects with asymptomatic cardiac toxicity	1	2	3	4			
Bayesian Posterior Prob[tox rate >20%]	0.82	0.85	0.88	0.90			
Subjects with symptomatic cardiac toxicity/heart failure	1	1	1	1			
Bayesian Posterior Prob[tox rate >5%]	>0.9	>0.9	0.91	0.86			

Subjects with vaccine-related DLT	2	3	4	5
Bayesian Posterior Prob[DLT rate >25%]	0.83	0.83	0.84	0.85
Action	Terminat	te accrual	, re-evalu	ate trial

6.9.5 Statistical Analyses and End of Trial Decision-making. Feasibility. A narrative of reasons why subjects could not complete treatment will be written. Safety. All graded toxicities will be tabled and described by frequency and percentage. Attribution to DC1 vaccine or trastuzumab will be assigned, if possible. All cardiac toxicities will be reported in detail. Toxicities observed during weekly vaccination will be tabled separately from toxicities observed during maintenance boosts. **Immunogenicity**. Immunogenicity will be evaluated by descriptive statistics, plots of pre- and post-treatment values and fold changes. Immune response rate and 95% exact confidence interval will be calculated. Anti-HER2 response will be quantitated as EOS/baseline fold change in dilution studies.

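### DLTs after a boost cannot trigger the only numeric vaccine-toxicity rule: section 6.9.3 counts the six weekly vaccines only, 6.9.4 has no boost boundary, and 6.7 D reads otherwise

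*Combined protocol and SAP*

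**What the plan says.** Section 6.9.3 fixes the counting window: "DLT rate will be defined by the weekly vaccination schedule. Toxicities will be scored separately for the maintenance boost schedule". Section 6.9.5 then tables boost toxicities separately and attaches no decision to them.

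Section 6.9.4 sets three boundaries: asymptomatic cardiac toxicity, symptomatic cardiac toxicity and vaccine-related DLT. For the last, "for vaccine-related DLT we assume a modestly informative beta (1, 3) prior", the limit is a 25% rate, and the boundary row at 3, 6, 9 and 12 treated reads "Subjects with vaccine-related DLT 2 3 4 5". There is no boost row, and none after 12 treated. On the consequence, the text says "Enrollment will be terminated if data indicate that the rate of" any of the three toxicities is above its limit. The table's action row pairs ending accrual with re-evaluating the trial.

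Section 6.7 D lists the DLTs with no reference to phase and says that a continuous monitoring rule for "dose-limiting toxicity will be followed during the trial, as described in section 6.11 Statistical Considerations". Statistical Considerations is section 6.9; there is no 6.11.

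The boosts are part of the planned treatment. Section 6.4.6 says: "Approximately 3 months from completion of the induction vaccines, subjects will receive 3 boost vaccines at approximately 3 month intervals". Section 6.9.1 is more conditional: subjects may become eligible for up to three.

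**The concern.** Safety is a primary objective (6.9.2), and 6.9.6 claims that the trial will firmly establish it. This is a single-arm trial with no dose escalation, so no next dose level depends on an early DLT window. The rule exists to detect unacceptable toxicity.

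If boost DLTs never enter the count, the trial can stay inside its DLT boundary while boost toxicity is frequent. The reported DLT rate then describes the weekly phase only. Supporting experience for the boost phase is also thin in the documents: earlier courses are described as 4 or 6 weeks of vaccination (1.0, 5.3), and no boost toxicity data are given.

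**Working it through.** **1. Share of treatment outside the rule.** 6 weekly + 3 boosts = 9 doses; 3/9 = 33%. If 18 subjects complete, 18 × 3 = 54 of 18 × 9 = 162 doses; this is a ceiling, since boosts are conditional in 6.9.1. Induction has five gaps of 8 to 21 days (6.4.6 D), so 40 to 105 days. The boosts fall at about 3, 6 and 9 months after it.

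**2. The plan's own figures.** With a Beta(1,3) prior and x DLTs in n subjects, the posterior is Beta(1 + x, 3 + n − x); the criterion is its upper tail beyond 0.25. For 2 of 3 this is Beta(3,4), whose tail equals P[Bin(6, 0.25) ≤ 2] = 0.178 + 0.356 + 0.297 = 0.831.

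| DLTs / treated | Plan | Recomputed |
|---|---|---|
| 2/3 | 0.83 | 0.831 |
| 3/6 | 0.83 | 0.834 |
| 4/9 | 0.84 | 0.842 |
| 5/12 | 0.85 | 0.852 |

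The figures reproduce. The gap is one of scope, not calculation.

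**3. How often the four-look rule triggers.** Exact sequential binomial enumeration over the looks 2/3, 3/6, 4/9 and 5/12 gives a cumulative probability of 0.009 at a 5% per-subject DLT rate, 0.039 at 10%, 0.30 at 25% and 0.68 at 40%. Only weekly-phase DLTs feed this.

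**4. Effect of leaving the boosts out.** The documents give no boost DLT rate, so the rates below are assumptions. Let w be the weekly-phase rate and b the boost rate among subjects without a weekly-phase DLT. The combined per-subject rate is 1 − (1 − w)(1 − b).

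| w | b | Combined | Trigger, weekly only | Trigger, boosts counted |
|---|---|---|---|---|
| 5% | 10% | 14.5% | 0.009 | 0.09 |
| 5% | 25% | 28.75% | 0.009 | 0.40 |
| 5% | 40% | 43% | 0.009 | 0.75 |
| 10% | 10% | 19% | 0.039 | 0.17 |
| 10% | 25% | 32.5% | 0.039 | 0.50 |
| 10% | 40% | 46% | 0.039 | 0.81 |

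The last column assumes that everyone is boosted and that boost outcomes are known at each look. It is optimistic, because the third boost comes about 9 months after induction. The weekly-only column does not depend on that assumption.

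**5. The binomial statement in 6.9.6** (at least 3 of 15) also reproduces: 0.764 at 25% and 0.184 at 10%. It does not say whether boost events count. With w = 5% and b = 25%, the probability of at least 3 of 15 is 0.036 if they do not and 0.85 if they do.

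**6. Past 12 treated.** The same posterior criterion gives 6/15 (0.861) and 7/18 (0.870); 5/15 gives only 0.718.

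**The case against.** The strongest defence is that the window was chosen deliberately and is coherent. Section 6.9.3 defines the treatment regimen for feasibility as the six weekly vaccines, boosts are conditional in 6.9.1, and 6.7 D defers to Statistical Considerations for the detail of the rule. That explains the window. It does not remove the conflict with 6.7 D, and no reason is given for leaving the boosts without a boundary.

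Boost toxicity is also not unwatched. A subject with grade 3 or greater toxicity leaves the protocol, apart from a fever exception, with no phase limit (6.7 D). DSMC milestones include two weeks after each boost for the first three subjects, with later frequency set after that review (6.6 H). The Moffitt PMC reviews adverse events monthly. The Safety Monitoring Committee may recommend suspension or termination (6.6 E). Cardiac toxicity is also assessed at end of study (6.9.3). All of this stands, but none of it is a numeric criterion for boost DLTs. Removal acts on one subject at a time, and its grade 3 wording does not cover a grade 2 autoimmune reaction, which 6.7 D lists as a DLT. LVEF is scheduled only at baseline and Booster 1, with later scans case by case (Appendix 1).

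A reader might infer two stronger things. One is that a triggered rule does no more than close enrollment. The action row also calls for the trial to be re-evaluated, so the documents do not support that. The other is that, since "Fifteen subjects were enrolled at Rowan Breast Center" and the cap is 18, the rule protects hardly anyone. That holds at most for the accrual stop as seen from version v2, where 18 − 15 = 3 places remain, or 17 − 15 = 2 on the 6.9.6 figure. Both counts set enrolled subjects against targets that 6.9.1 and 6.9.6 state as evaluable, and the number evaluable among the 15 is not given. The looks at 3 to 12 treated were prospective for earlier subjects, and re-evaluation can reach enrolled women with doses still due.

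**Conclusion.** The point holds as a gap in scope. Under 6.9.3 and 6.9.4, a DLT after a boost cannot trigger the only numeric vaccine-toxicity rule, and 6.7 D conflicts with that restriction. Up to a third of the doses and about 9 months of dosing are affected. That the boosts cannot move the trigger probability follows from the text alone. The size of the loss (for example 0.009 against 0.40) rests on assumed rates and on boost outcomes being available at each look, so it is an upper figure.

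Two smaller gaps go with it. The table stops at 12 treated although 15 were enrolled at this version. And neither the text nor the action row says what happens to doses still due in enrolled subjects.

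**What to change.** Reconcile 6.7 D, 6.9.3 and 6.9.4, correct the reference to 6.11, and put boost DLTs under a stated boundary in one of two ways:

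- **A separate boost row**, with the same Beta(1,3) prior and 25% limit, among subjects who received a boost. The boundary counts are then the same as in the existing row. Both rows can stay silent while the combined rate exceeds 25%: two rates of 20% combine to 1 − 0.8 × 0.8 = 36%. The prior was justified by the DCIS trials, so its use for boosts needs a sentence of support.
- **A pooled row**, counting each subject once for a DLT after any vaccine through 30 days after her last dose. The separate weekly and boost tables remain as description.

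Either way, extend the table to 6/15 and 7/18, say whether the 6.9.6 statement includes boost events, and restate the operating characteristics.

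The cost is an amendment and some recalculation. No new data are needed: adverse events are already collected at every boost visit (Appendix 1), and 6.9.1 already follows subjects for 30 days after the final vaccination. The real downside is more triggering. At 10% weekly plus 10% boost (19% combined, still under the limit), the pooled rule triggers with probability 0.17 instead of 0.039 if boost outcomes are known at each look. With separate rows, treated as independent and with 12 boosted subjects, the chance that either triggers is about 1 − (1 − 0.039)² = 0.08. Subjects with incomplete boost follow-up must not count in the denominator as if fully observed, so the plan must say how they are handled.

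Separately, the sponsor should reconcile the enrollment text with the action row as to doses still due in enrolled subjects. Which clinical rule applies is for the sponsor.

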12.0 RISK/BENEFIT RATIO	
13.0 REFERENCES	

1.0 Purpose

We have demonstrated that administration of HER-2/neu pulsed DC1 in patients with DCIS and early invasive breast cancer (IBC) results in strong immunologic responses as well as apparent clinical responses during 4 and 6 week neoadjuvant vaccination. Patients with locally advanced breast cancer that have significant nodal disease have significant risk of systemic recurrence. In addition, those patients with recurrence after chemotherapy and trastuzumab have significant risk of additional local or systemic recurrence and may be resistant to trastuzumab. Those patients with HER-2 2+ that are FISH negative that are often ER positive with significant nodal disease are also at high risk for recurrence despite chemotherapy and anti-estrogen therapy. These patients are not classically treated with trastuzumab but may still respond to HER-2 directed therapy but also have diminished immunity to HER-2. All these patients have little additional therapy options. We hypothesize that adding DC1 vaccines pulsed with HER-2, will reduce the risk of recurrence and diminish deaths in these high risk patients. The primary goals of this trial will be to determine the safety and immune activity of HER-2 pulsed DC1 vaccine in patients with high risk HER-2^{pos} breast cancer with significant risk of systemic recurrence. We will also explore the possibility of determining whether circulating tumor cells can be used as surrogate to assess response to vaccination.

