6.9.6 Sample Size Justification and Study Duration. This phase I trial will enroll 17 evaluable subjects over 1.5 years and will firmly establish feasibility and safety of DC1 vaccination. In addition to Bayesian posterior probabilities for toxicities, binomial probability statements will also inform our decision-making. For example, a treatment may be considered excessively toxic if \geq 3 of 15 subjects exhibit unacceptable vaccine-related toxicity. This rule yields at least 0.76 probability of correctly judging the treatment as excessively toxic if the true toxicity rate is >25%, with no more than 0.18 probability of incorrectly judging the treatment as excessively toxic if the true toxicity rate is <10%.

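### Feasibility is a primary objective but gets only a narrative, with no completion proportion, denominator or interval, and the number of evaluable subjects cannot fill that gap alone

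*Combined protocol and SAP*

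**What the plan says.** Section 6.9.2 states: "The primary objectives are to determine feasibility and safety". Section 6.9.3 defines feasibility as a subject's "ability and willingness to complete the treatment regimen (6 weekly vaccinations"), which is a yes/no outcome for each subject.

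Section 6.9.5 gives each endpoint its analysis:
- Feasibility: "A narrative of reasons why subjects could not complete treatment will be written". Nothing more is planned.
- Safety: "All graded toxicities will be tabled and described by frequency and percentage".
- Immune response, a secondary objective: "Immune response rate and 95% exact confidence interval will be calculated".

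Section 6.9.6 says that a trial of 17 evaluable subjects "will firmly establish feasibility and safety of DC1 vaccination". The term is defined in 6.9.1: "Evaluable implies that a subject received all 6 weekly vaccinations and underwent leukapheresis after the vaccinations for immune response evaluation". Section 2.0 has the same definition.

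The sizes differ. Sections 2.0 and 6.9.1 aim for 18 evaluable subjects, 6.9.6 for 17 evaluable, and 6.2 allows no more than 18 enrolled. On timing, 6.9.3 counts six weekly doses, while 6.4.6 D describes a weekly intention but permits 8 to 21 days between the first six.

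**The concern.** A primary objective with a binary outcome would normally be answered by a proportion, a stated denominator and an interval. Here it gets less analysis than a secondary endpoint in the same paragraph. With no denominator fixed in advance, completion could later be reported out of those consented, those who had leukapheresis or those first dosed, and the choice could be made after the data are seen.

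Section 6.9.6 then claims a firm answer on feasibility from a group selected for having completed. At stake is whether the trial can state a completion rate, with its uncertainty, that a reader can check.

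**Working it through.** **1. The plan's own figures, and what they concern.** Section 6.9.6 gives operating figures for one rule only: call the treatment excessively toxic if at least 3 of 15 subjects have unacceptable vaccine-related toxicity. With X binomial(15, p), P(X ≥ 3) = 1 − P(0) − P(1) − P(2).
- p = 0.25: 1 − (0.0134 + 0.0668 + 0.1559) = 0.764 (stated: at least 0.76).
- p = 0.10: 1 − (0.2059 + 0.3432 + 0.2669) = 0.184 (stated: no more than 0.18; agrees to two decimals).

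Both figures reproduce, and both concern toxicity, as do the posterior probabilities in 6.9.4. No figure in 6.9 concerns completion, and no calculation is shown that leads to 17.

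**2. What a count of evaluable subjects says about completion.** Evaluable means six vaccinations received plus a leukapheresis afterwards. Completion among evaluable subjects is therefore 100% whatever the true rate. Information on completion comes only from comparing completers with the number who enrolled or started.

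**3. What the stated sizes allow.** Take 18 as the enrolment cap (6.2). A target of 18 evaluable leaves 18 − 18 = 0 possible non-completers. A target of 17 leaves at most 18 − 17 = 1.

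**4. Attainable precision.** Exact (Clopper-Pearson) 95% limits for x completers of n enrolled:
- Lower limit: the 2.5% quantile of beta(x, n − x + 1).
- Upper limit: the 97.5% quantile of beta(x + 1, n − x), or 1 when x = n.

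| Completers / enrolled | Proportion | Exact 95% interval | Width (points) |
|---|---|---|---|
| 18/18 | 100% | 81.5% to 100% | 18.5 |
| 17/18 | 94.4% | 72.7% to 99.9% | 27.2 |

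For 18/18 the lower limit is 0.025^(1/18) = 0.815.

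**5. If 18 is not a cap on enrolment.** Sections 2.0, 6.9.1 and 6.9.6 can be read as accruing until the evaluable target is met. The number started is then open. The values below are assumptions; the documents give no expected dropout.

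| 17 completers out of (assumed) | Proportion | Exact 95% interval |
|---|---|---|
| 20 | 85.0% | 62.1% to 96.8% |
| 22 | 77.3% | 54.6% to 92.2% |
| 25 | 68.0% | 46.5% to 85.1% |

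The same 17 completers fit quite different completion rates. These intervals treat the number started as fixed, so they are illustrations only.

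**The case against.** The best defence is that this is a small single-arm pilot. The narrative requires non-completers to be identified, so anyone with the enrolled and completed counts can compute the rate and its interval. No feasibility threshold is stated, so no decision is shown to change, and no stopping rule depends on it. All of that stands, and it limits the point to a reporting gap and one unsupported statement. It does not supply a rate or a denominator that the plan commits to in advance.

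A reader might also infer more than the documents support:
- *That feasibility will be analysed on the evaluable set.* The plan never says so. The circularity lies in the 6.9.6 statement, and evaluable counts become informative once the number started is reported with them.
- *That subjects are known to be lost to poor cell yield or failed release.* Section 6.1.1 provides for a further collection, and 6.4.3 for re-making a vaccine that misses the viability cutoff. Loss before the first dose remains possible, but no such loss is documented and no rate is given.
- *That a strict weekly reading would leave nobody dosed within the permitted spacing counted as a completer.* Section 6.4.6 D expressly allows that spacing. The definition needs tidying; the endpoint is not emptied.
- *That much lower completion, such as 14 of 18, is what the plan implies.* Under a cap of 18, that result would miss the plan's own evaluable target.

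**Conclusion.** The concern holds as a missing analysis for a primary objective, together with a claim in 6.9.6 that nothing in the plan supports. No printed figure is wrong.

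If 18 is the enrolment cap and the evaluable target is met, completion can be estimated no more precisely than 81.5% to 100% (all 18 complete), or 72.7% to 99.9% with one non-completer. Those limits are useful for a pilot but do not justify describing feasibility as firmly established. If 18 is not a cap, the range is wider and depends on a number started that the documents do not give.

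Two inconsistencies bear directly on this: the three statements of sample size, because they decide how many non-completers the plan can accommodate, and the two descriptions of dose spacing, because they decide what counts as completed. The completion rate does not depend on whether post-vaccination leukapheresis is mandatory, on the primary goals named in section 1.0, or on the denominator of the toxicity rule. Those are separate matters.

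**What to change.** - **6.9.5:** report the number and proportion of subjects completing six vaccinations, with an exact 95% confidence interval, among all enrolled subjects and, secondarily, among all who received vaccine 1. Keep the narrative of reasons, and list any loss before the first dose separately.
- **6.9.6:** replace the claim that feasibility will be firmly established with the attainable precision, for example 81.5% to 100% for 18/18 and 72.7% to 99.9% for 17/18.
- **2.0, 6.2, 6.9.1 and 6.9.6:** reconcile 18 evaluable, 17 evaluable and at most 18 enrolled, and say whether 18 is a limit on enrolment.
- **6.9.3 and 6.4.6 D:** reconcile the two descriptions of spacing so that completion has a single meaning.

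The cost is a few sentences of text and two proportions with intervals, computed from enrolment and dosing records the trial needs anyway. The sample size does not change and no test is added. The downside is a wide interval and a feasibility figure that may look less favourable than a narrative.

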2.0 Duration of Study

This study will enroll 18 evaluable subjects over 1.5 years averaging 10 subjects per year. Evaluable implies that a patient received all 6 vaccinations and underwent leukapheresis after the vaccinations for immune response evaluation.

Fifteen subjects were enrolled at the Rowan Breast Center. Approximately 4 subjects will receive their treatment at follow up at Moffitt Cancer Center while remaining subjects will continue to be followed at Rowan Breast Center.

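### Planned size is 17 evaluable in 6.9.6 but 18 evaluable in 2.0 and 6.9.1, and the example toxicity rule gives its error rates only for an unexplained 15 subjects

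*Combined protocol and SAP*

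**What the plan says.** The combined protocol and SAP gives the planned size in four places.

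- Section 2.0: "This study will enroll 18 evaluable subjects over 1.5 years".
- Section 6.2: "Up to 18 patients will be enrolled in this Pilot Phase I trial".
- Section 6.9.1: "This study will enroll 18 evaluable subjects".
- Section 6.9.6: "This phase I trial will enroll 17 evaluable subjects over 1.5 years".

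Sections 2.0 and 6.9.1 both define an evaluable subject as one who has had all six vaccinations and a leukapheresis afterwards. Evaluable is therefore a narrower count than enrolled or treated.

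Section 6.9.6 adds that "binomial probability statements will also inform our decision-making", alongside the Bayesian posterior probabilities of 6.9.4. As an example, the treatment may be judged excessively toxic if at least "3 of 15 subjects exhibit unacceptable vaccine-related toxicity". The properties given are "This rule yields at least 0.76 probability of correctly judging the treatment as excessively toxic if the true toxicity rate is >25" per cent, and "with no more than 0.18 probability of incorrectly judging the treatment as excessively toxic if the true toxicity rate is <10" per cent. The table in 6.9.4 counts subjects treated and stops at 12.

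**The concern.** Sections 6.9.1 and 6.9.6 belong to the same statistical chapter and disagree on the number of evaluable subjects. The cap in 6.2 is in different units, but it still interacts with the target: if 18 evaluable are required and at most 18 may enrol, every enrolled subject must turn out evaluable.

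The sample size justification then rests on a rule with denominator 15. The text does not say whether these are the first 15 treated, 15 evaluable subjects or something else, and it gives no probabilities for 17 or 18. Safety is a primary objective, and 6.9.6 says that such binomial statements will feed into decisions. A reader who applies the cut-off of 3 to the whole trial would be working with error rates that the plan does not report.

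**Working it through.** **Inputs.** Rule: flag if at least 3 subjects have unacceptable toxicity, n = 15 (6.9.6). True rates: p = 0.25 and p = 0.10 (6.9.6). Planned sizes: 17 (6.9.6) and 18 (2.0, 6.9.1). The flag probability rises with p, so 0.25 and 0.10 are the limiting cases for rates above 25% and below 10%.

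**Formula.** P(flag) = P(X ≥ c) = 1 − Σ C(n, x) pˣ (1 − p)ⁿ⁻ˣ, summed over x = 0 to c − 1.

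**Plan's own figures, n = 15, c = 3.**
- p = 0.25: 1 − (0.0134 + 0.0668 + 0.1559) = 0.7639.
- p = 0.10: 1 − (0.2059 + 0.3432 + 0.2669) = 0.1841 (the unrounded terms sum to 0.8159).

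These round to the stated 0.76 and 0.18, so the pair is right for 15.

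**Same formula at other treated numbers.**

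| Treated | Cut-off | P(flag) at 25% | P(flag) at 10% |
|---|---|---|---|
| 15 | at least 3 | 0.764 | 0.184 |
| 17 | at least 3 | 0.836 | 0.238 |
| 17 | at least 4 | 0.647 | 0.083 |
| 18 | at least 3 | 0.865 | 0.266 |
| 18 | at least 4 | 0.694 | 0.098 |

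**How often the reading of the 15 changes the verdict, cut-off 3.** A count of 3 or more in the first 15 is also 3 or more in the full set. The two readings therefore differ only when the third event falls after subject 15, and the probability of that is the difference of the two tails.
- 17 treated: 0.2382 − 0.1841 = 0.054 at 10%; 0.8363 − 0.7639 = 0.072 at 25%.
- 18 treated: 0.2662 − 0.1841 = 0.082 at 10%; 0.8647 − 0.7639 = 0.101 at 25%.

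**Evaluable against treated.** Section 6.7 D takes subjects with toxicity of grade 3 or higher off protocol, with an exception for fever. A subject to whom this happens before the sixth vaccination has been treated but is not evaluable. If the evaluable target is reached by replacing such subjects, the treated number exceeds 17 or 18. For illustration, with 20 treated (an assumed number), at least 3 gives 0.909 / 0.323 and at least 4 gives 0.775 / 0.133.

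**Enrolment cap.** 18 − 17 = 1 non-evaluable subject can be absorbed if 17 evaluable are required; 18 − 18 = 0 if 18 are required.

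**The case against.** The strongest reply is that 0.76 and 0.18 are not wrong. They are attached to a rule on 15 subjects, they are correct for it, and the plan nowhere presents them as properties of the full trial. The rule is offered as an example, in permissive wording, and comes on top of the Bayesian table. This stands. A reader might infer that the probabilities are miscalculated; they are not, and 0.1841 against a stated maximum of 0.18 is rounding.

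A reader might also infer that the plan fails its own requirements. At 17 or 18 treated, a cut-off of 3 exceeds 0.18 and a cut-off of 4 falls short of 0.76. Both probabilities fall as the cut-off rises, so no cut-off keeps both figures. The arithmetic is right at those two sizes, but the documents give 0.76 and 0.18 as what the example yields, not as targets, and with 20 treated a cut-off of 4 would satisfy both.

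A deliberate reading of 15 is possible. Reviews are expected after groups of three, so 15 is the next step after 12. It also equals 10 subjects a year for 1.5 years, and the fifteen subjects enrolled at the first site. No passage connects the rule to any of these, so the reading remains a guess. One clause would settle it.

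Finally, the cap in 6.2 is not a third conflicting sample size. It counts enrolled subjects and is compatible with 17 evaluable. The direct contradiction is 17 against 18, a difference of one subject. That is small, but no passage resolves it.

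**Conclusion.** The point holds as an inconsistency in the planned number together with a gap in the justification. Seventeen and 18 evaluable cannot both be the plan, and 18 evaluable under a cap of 18 allows no loss. The stated pair 0.76 / 0.18 describes 15 subjects only; at cut-off 3 it becomes 0.84 / 0.24 with 17 treated or 0.86 / 0.27 with 18 treated.

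The size is minor to moderate. Keeping 3 at a larger number raises false flags but also detection, so any error is on the cautious side. The choice between the first 15 and all subjects changes the verdict with probability 0.05 to 0.10 at the two rates considered. The Bayesian stopping table for 3 to 12 treated is untouched, and the documents give no support for inferring that safety monitoring is compromised.

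The figures assume independent subjects with a common toxicity rate, the rule applied alone without earlier stops under 6.9.4, and a treated number equal to the one shown. They would not apply if non-evaluable subjects were replaced.

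**What to change.** 1. Reconcile Sections 2.0, 6.2, 6.9.1 and 6.9.6 to one evaluable number and one enrolment cap that are compatible with each other.
2. In 6.9.6, state the number of treated subjects to which the example rule applies, and give the exact binomial probabilities (at 25% / at 10%) for that number:
   - first 15 treated: 0.76 / 0.18 for at least 3;
   - 17 treated: 0.84 / 0.24 for at least 3, or 0.65 / 0.08 for at least 4;
   - 18 treated: 0.86 / 0.27 for at least 3, or 0.69 / 0.10 for at least 4.
3. If the evaluable target is met by replacing subjects, recompute at the larger treated number.

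The cut-off is for the sponsor to choose. The cost is wording in four sections. If the rule is restated at 17 or 18, one reported figure becomes less favourable: the false-flag probability with at least 3, or detection with at least 4. If it is tied to the first 15, the stated pair stays, but later subjects fall outside the example.
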